7.3.2 Secondary endpoint analyses

7.3.2.1 Analyses of the key secondary endpoints

The key secondary endpoints of the absolute change from baseline in mRSS at week 52, and the absolute change from baseline in the SGRQ total score at week 52, will be analysed using a restricted maximum likelihood (REML) based repeated measures approach. Analyses will include the fixed, categorical effects of treatment, ATA status, visit, and treatment-by-visit interaction, as well as the continuous, fixed covariates of baseline and baseline-by-visit interaction. An unstructured (co)variance structure will be used to model the within patient measurements.

If this analysis fails to converge, the following covariance structures will be tested in order: heterogenous toeplitz, toeplitz and autoregressive 1 (AR[1]). The first model to converge will be used. The Kenward-Roger approximation will be used to estimate denominator degrees of freedom. Significance tests will be based on least-squares means using a two-sided $\alpha = 0.05$ (two-sided 95% confidence intervals [CIs]). In case the model fails to converge under PROC MIXED, the "singular" option will be considered. The treatment comparisons will be the contrast between treatments at week 52. An intent-to-treat principle will be used (i.e. all available data up to 52 weeks will be used, including data for patients who prematurely discontinue randomised treatment).

The effect of missing data will be investigated using multiple imputation methods which assume that patients who discontinue treatment will no longer benefit from it in the future. See Section 7.5.1 for further details. Additional sensitivity analyses and subgroup analyses may be done and will be described in the TSAP.

A cumulative distribution plot will be provided, showing the percentage of patients by the change from baseline in mRSS at week 52.

7.3.2.2 Analyses of the other secondary endpoints

The rate of decline in FVC in percent predicted will be analysed in the same way as the primary endpoint including ATA status and baseline FVC% predicted as covariates. All other continuous secondary endpoints will be analysed in the same way as the key secondary endpoints using a MMRM approach.

Proprietary confidential information © 2018 Boehringer Ingelheim International GmbH or one or more of its affiliated companies

If the percentage of deaths during the trial is less than 2% in total, then the number and percentage of deaths will be presented by treatment group. Otherwise, a Cox proportional hazards model stratified by ATA status will be used to estimate and test (based on a Wald test) the hazard ratio of nintedanib vs placebo for the time to all-cause mortality endpoint. A Kaplan-Meier plot by treatment group will also be presented. Note that the endpoint will be based on all available data collected up to trial completion.

Any p-values presented for the secondary endpoints (with the exception of the key secondary endpoints) will be considered nominal in nature and no adjustment for multiplicity will be made.

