3.3 SELECTION OF TRIAL POPULATION

A sufficient number of patients of either sex, 18 years of age or older, with a diagnosis of SSc-ILD will be enrolled in the trial (see Section 7.7 for sample size details). All patients are expected to be randomised in about 18 months of overall trial initiation (i.e. initiation of the first site).

The enrolment will be competitive.

No sufficient scientific data are currently available to either rule out or confirm efficacy of stable immunosuppressive treatment at baseline (mycophenolate or methotrexate), as allowed per protocol, for the enrolled study population. To be able to assess the treatment effect of nintedanib versus placebo in patients without mycophenolate or methotrexate background medication in the trial, recruitment of patients on stable dose of such background treatment may be restricted.

A maximum of 520 patients will be recruited by approximately 230 sites in about 33 countries worldwide. Sites will be experienced in the management of patient with SSc-ILD and are each expected to include approximately 3 patients.

Additional sites may be initiated and 'non-productive' sites may be closed to ensure sponsor's timelines.

A log of all patients enrolled into the trial (i.e. who have signed informed consent) will be maintained in the Investigator's site file (ISF) at the investigational site irrespective of whether they have been treated with investigational drug or not.

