7.6 RANDOMISATION

Patients will be randomised in blocks to double-blind treatment. The randomization will be stratified by ATA status (positive or negative) within the IRT system. Approximately equal numbers of patients will be randomised to each treatment group (i.e. a 1:1 randomisation will be used). BI will arrange for the randomization and the packaging and labelling of trial medication. The randomisation list will be generated using a validated system, which involves a pseudo-random number generator so that the resulting treatment will be both reproducible and non-predictable. The block size will be documented in the clinical trial report. Access to the codes will be controlled and documented. All members of the clinical trial team will remain blinded to the randomization schedule until the final database is locked. The independent DMC will at any time have the possibility to look at unblinded data according to the DMC charter.

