Similar analyses as for the first key secondary endpoint (Absolute change from baseline in the mRSS) will be performed for the absolute change in SGRQ total score, in the TS. Please refer to [Section 7.5.1.1](#).

Note that for the imputation of SGRQ total score missing values, imputed values will be truncated if needed so that they are comprised between 0 and 100.

In addition, a cumulative distribution plot of the absolute change from baseline in SGRQ total score at week 52 will be provided.

7.5.2 (Other) Secondary endpoint(s)

No sensitivity or subgroup analyses will be performed on the following other secondary endpoints. These will be analysed on the TS.

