7.5.2.4 Time to death

Please refer to CTP Section 7.3.2.2 for the summary of analyses and [Section 5.2.2.2](#) for the definition of the censoring.

A Kaplan-Meier plot of time to death over the whole trial duration will be displayed. Time to death at Week 52 will also be displayed as additional information.

7.5.2.5 CRISS index score at week 52

For all analyses, please note that CRISS index represents a probability of improvement and ranges between 0 and 1.

Descriptive statistics summarizing CRISS value at 52 weeks will be provided by treatment group.

The cumulative proportion of patients whose probability of improving at week 52 with regard to their CRISS index will be shown by using a broad range of cut-offs for the CRISS value at 52 weeks (≥ 0 , ≥ 0.1 , ≥ 0.2 , ..., $\geq 0.9, 1$), in a cumulative proportion of responder analysis

graph (19). The proportion of patients showing improvement for CRISS based on each cut-off will also be tabulated.

In order to analyse CRISS index across both treatment groups, it will be transformed into a binary responder endpoint using multiple imputation. More specifically, the following steps will be applied:

- For each patient, 100 random uniform draws in the range from 0 to 1 will be taken
 - If the value of the draw $>$ CRISS index value of the patient then the responder variable will be set to « No » for that patient
 - If the value of the draw \leq CRISS index value of the patient then the responder variable will be set to « Yes » for that patient
- This results in 100 imputed datasets including a responder variable for each of the patients that indicates whether or not this patient is considered a responder or not, as derived from the actual CRISS index of the patient
- For each complete dataset of patients obtained by imputation as described above, the comparison between both treatment groups regarding the newly obtained binary will be performed using a Cochran-Mantel-Haenszel (CMH) model adjusting for ATA status. Adjusted Mantel-Haenszel odds ratio (OR) with 95% confidence intervals (CI) will be used to quantify the treatment effect between the Nintedanib group and Placebo.

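### The Wald test for time to death breaks down if all deaths fall in one arm; a stratified log-rank test with a profile-likelihood interval avoids this at almost no cost (low weight)

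*Protocol*

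**What the plan says.** Protocol 7.3.2.2 sets a two-branch rule for time to all-cause mortality.

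- **Low branch:** "If the percentage of deaths during the trial is less than 2% in total, then the number and percentage of deaths will be presented by" arm.
- **High branch:** "a Cox proportional hazards model stratified by ATA status will be used to estimate and test (based on a Wald test) the hazard ratio", together with a Kaplan-Meier plot.

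The same section bases the endpoint on the whole trial ("Note that the endpoint will be based on all available data collected up to trial completion") and makes p-values for non-key secondary endpoints nominal, without multiplicity adjustment.

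SAP 7.5.2.4 adopts the rule: "Please refer to CTP Section 7.3.2.2 for the summary of analyses". It adds a Kaplan-Meier plot with no 2% condition, and names no other test and no interval. SAP Section 4 only renames the endpoint. The non-convergence steps in SAP 7.4.1 and 7.5.1.1 are for the mixed models. Neither document says what to do if the hazard ratio is not finite.

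**The concern.** The Wald statistic divides the estimated log hazard ratio by its standard error. With few events, the standard error grows faster than the estimate as the split between arms becomes more extreme. When one arm has no deaths, the estimate runs to infinity and the ratio collapses towards zero. The test then reports almost no evidence for the split that carries the most.

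The 2% rule shows that the sponsor foresaw low death counts, and it switches the Wald test on where this weakness is greatest. Time to death is a pre-specified secondary endpoint and the only planned between-arm test of survival alone. The failure is symmetric, so it applies to benefit and to harm. If the case arose, a replacement method would have to be chosen after seeing the data.

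**Working it through.** **Inputs.** Total N = 520 (Protocol 3.3: "A maximum of 520 patients will be recruited by approximately 230 sites"), 1:1 allocation (Protocol 7.6), and the 2% trigger and Wald test (Protocol 7.3.2.2). The documents give no expected death count, hazard ratio or power for mortality, so the trigger is the only plan figure to reproduce.

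**Trigger.** 10/520 = 1.92% and 11/520 = 2.12%, so the test starts at 11 deaths. The rule does not name its denominator. SAP 7.5.2 uses the treated set ("These will be analysed on the TS"), but the trigger is 11 for any N from 501 to 550, so a few undosed patients do not move it.

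**Approximation.** With rare events and equal follow-up, given D deaths, the number x in one arm is Binomial(D, HR/(1+HR)). Then:

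- Wald: z = ln(x/(D−x)) / √(1/x + 1/(D−x))
- Score (log-rank): z = (x − D/2) / (√D/2)
- Exact: two-sided binomial with probability 1/2

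Example, 2:9. Wald: ln(2/9) = −1.504; √(1/2 + 1/9) = 0.782; z = −1.92; p = 0.054. Score: (2 − 5.5)/1.658 = −2.11; p = 0.035.

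| Split | Wald p | Score p | Exact p |
|---|---|---|---|
| 0:11 | → 1 | 0.0009 | 0.0010 |
| 1:10 | 0.028 | 0.007 | 0.012 |
| 2:9 | 0.054 | 0.035 | 0.065 |
| 3:8 | 0.147 | 0.132 | 0.227 |
| 1:19 | 0.0041 | 0.0001 | <0.0001 |
| 2:18 | 0.0032 | 0.0003 | 0.0004 |

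At 20 deaths the Wald p-value is larger for 1:19 than for the less extreme 2:18.

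**Check with fitted models.** ATA-stratified Cox models were fitted to simulated data (260 per arm, censoring uniform over 52 to 100 weeks, 60 data sets per split). The ATA-positive share is not in the documents, so 40%, 60% and 80% were assumed; results barely differ.

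- 0:11: log hazard ratio about −22 at stopping, standard error about 20,000, Wald p = 0.999, score p about 0.0008, likelihood-ratio p about 0.0001.
- 1:10: Wald about 0.027, score about 0.006.
- 2:9: Wald about 0.053, score about 0.034.
- 3:8: Wald 0.14, score 0.13, likelihood ratio 0.12.
- 0:12, 0:16 and 0:20: Wald p still 0.999.

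**How likely is 11:0?** P = (HR/(1+HR))^11 + (1/(1+HR))^11. This gives 0.1% at HR 1, 0.3% at 0.7, 1.2% at 0.5, 5.6% at 0.3 and 35% at 0.1.

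**What the replacement interval gives at 11:0.** The log-likelihood is −11·ln(1+r), with supremum 0. The 95% profile limit solves 22·ln(1+r) = 3.84, so r = e^0.1746 − 1 = 0.19. That is a finite upper bound where Wald gives none. The exact conditional interval is wider, 0 to 0.40.

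**Size of the score test.** Under HR 1, D = 11 rejects at x ≤ 2 or x ≥ 9: 2 × (1+11+55)/2048 = 6.5%. D = 16 rejects at x ≤ 4 or x ≥ 12: 2 × 2517/65536 = 7.7%. For every D from 11 to 30, the score test rejects each split that Wald rejects.

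**The case against.** **Most lopsided splits are still detected.** A reader might infer that any one-sided death pattern would come out non-significant. It would not: 1:10 gives Wald p = 0.028 and 1:19 gives 0.0041. The reversal between 1:19 and 2:18 changes no conclusion. The hard failure is confined to an arm with no deaths. This stands.

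**Few deaths may not occur.** Protocol 1.1 cites a median survival of 5–8 years in SSc-ILD. Under a constant hazard, one-year mortality is 1 − 0.5^(1/8) = 8.3% to 1 − 0.5^(1/5) = 12.9%, or about 43 to 67 of 520. Eligibility may select lower-risk patients, so this is rough, but it lies well above the range at issue. This stands, and it lowers the weight.

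**Nothing confirmatory depends on it.** The endpoint is outside the testing hierarchy and its p-value is nominal. This stands.

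**Harm does not rest on this p-value.** A reader might infer that a mortality imbalance could go unseen, or that below 2% only counts appear. The documents do not support either. The SAP plans an unconditional Kaplan-Meier plot, tables of adverse events leading to death, adjudicated cause of death by arm, and incidence rates per 100 patient-years. The DMC can see unblinded data. Below 2% what is missing is an interval or test, and withholding inference at 10 deaths or fewer is a defensible pre-specified choice.

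**An exact test is not simply better.** One might go further and ask for an exact p-value whenever deaths are few. At 14 deaths and HR 0.2, exact power is 58% against 73% for Wald (size 1.3% against 5.7%). This stands, and it rules out the exact test as the main analysis.

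None of this answers the remaining defect: under complete separation the named test returns a wrong p-value and an unusable interval, and no fallback is written down.

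**Conclusion.** The point holds as a low-weight correction. From 11 deaths, the planned test gives p of about 1 and an unbounded interval if one arm has no deaths, where score and exact tests give about 0.001. At 2:9 it falls on the other side of 0.05 from the score test (0.054 against 0.035), although the exact test does not reject there either (0.065). The practical chance of harm is small: about 1% for 11:0 at HR 0.5, and lower with more deaths.

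The result rests on N close to 520. The table values also assume rare events and equal follow-up, and the fitted Cox models agree with them closely. The divergence itself needs no such assumption. The exact Wald p-value depends on the software's stopping rule but tends to 1 under any usual one.

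**What to change.** In SAP 7.5.2.4, as a stated change from Protocol 7.3.2.2, replace the Wald test with the ATA-stratified log-rank (score) test. Keep the stratified Cox estimate and report a profile-likelihood 95% CI for the hazard ratio, with a one-sided bound if an arm has no deaths. An exact or permutation p-value may be added as a supplement when deaths are few, but not as the main test. Keep the 2% rule and the nominal status.

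The cost is one sentence and a few procedure options, with no patients and no data. The downside is that the score test can exceed its nominal size at some very small counts (about 6.5% at 11 deaths and 7.7% at 16 under the approximation above), which is tolerable for a nominal p-value and should be acknowledged.

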7.3.3 Further endpoint analyses

All further endpoints will be summarized descriptively and will be considered exploratory in nature.

Baseline levels and changes from baseline in serum and plasma protein biomarkers will be summarized descriptively over time by treatment group. Correlations between change from baseline in clinical measures (FVC, mRSS) and serum/plasma and RNA biomarker levels will be explored. In addition, the relationships between drug concentrations, clinical efficacy and selected biomarkers will be explored. The results may be included in a separate biomarker analysis plan and report.

7.3.4 Safety analyses

Adverse events will be coded using the Medical Dictionary for Regulatory Activities (MedDRA) coding dictionary. Standard BI summary tables and listings will be produced. All treated patients will be included in the safety analysis. In general, safety analyses will be descriptive in nature and will be based on BI standards. No hypothesis testing is planned.

Statistical analysis and reporting of adverse events will concentrate on treatment-emergent adverse events. To this end, all adverse events occurring between start of treatment and end of the residual effect period will be considered 'treatment-emergent'. The residual effect period is the 28 days after the date of the last dose of trial medication. Adverse events that start before first drug intake and deteriorate under treatment will also be considered as 'treatment-emergent'. Based on the half-life of the study drug, adverse events that occur between the start of treatment and up to 7 days after the date of the last dose of trial medication will be analysed in addition.

Frequency, severity, and causal relationship of adverse events will be tabulated by system organ class and preferred term after coding according to the current version of the MedDRA.

Laboratory data will be analysed both quantitatively as well as qualitatively. The latter will be done via comparison of laboratory data to their reference ranges. Values outside the reference range as well as values defined as clinically relevant will be highlighted in the

Proprietary confidential information © 2018 Boehringer Ingelheim International GmbH or one or more of its affiliated companies

listings. Treatment groups will be compared descriptively with regard to distribution parameters as well as with regard to frequency and percentage of patients with abnormal values or clinically relevant abnormal values.

Vital signs, physical examinations, or other safety-relevant data observed at screening, baseline, during the course of the trial and at the end-of-trial evaluation will be assessed with regard to possible changes compared to findings before start of treatment.

7.3.5 Pharmacokinetic analyses

In the CTR, pre-dose plasma concentrations (Cpre,ss) of nintedanib and its two metabolites (BIBF 1202 and BIBF 1202-glucuronide) will be tabulated with descriptive statistics.

For pharmacokinetic analysis and displays, concentrations will be used in the same format as reported in the bio-analytical report. Only concentrations within the validated concentration range and actual sampling times will be used. See Appendix 10.6.1 for further details.

7.4 INTERIM ANALYSES

Safety data will be reviewed on a regular basis by a DMC (see the DMC charter for further details). A blinded assessment of variability and/or rate of FVC decline may be performed in order to check and re-estimate the sample size assumptions. More details regarding the timing and the recalculation strategy will be provided in the TSAP and will be available by the time of first patient in. No unblinded interim analyses are planned.

7.5 HANDLING OF MISSING DATA

7.5.1 Efficacy endpoints

The effect of missing data on the primary endpoint will be investigated using multiple imputation techniques.

For the primary endpoint, the following subsets of patients will be defined:

- 1) Patients with an FVC result at week 52 who received trial medication until week 52.
- 2) Patients with an FVC result at week 52 who prematurely discontinued trial medication prior to week 52.
- 3) Patients without an FVC result at week 52 who were alive at week 52.
- 4) Patients without an FVC result at week 52 who died prior to week 52.

These four subsets of patients will be used in sensitivity analyses to estimate the treatment effect under differing assumptions around the persistence of efficacy after withdrawal of trial medication. Table 7.5.1: 1 describes the planned sensitivity analyses for handling missing primary endpoint data. Sensitivity analyses 1 and 2 will only be performed if there are at least 10 patients included in patient subset 2 in each treatment group.

Trial Protocol

Table 7.5.1: 1 Sensitivity analyses for handling missing primary endpoint data

Analysis		et 3: No FVC result but we at Week 52		set 4: No FVC result and prior to Week 52
	Handling of missing FVC result	Underlying assumption	Handling of missing FVC result	Underlying assumption
Primary analysis	Missing data handled by model.	Assumes missing at random. Discontinued patients would have behaved similarly to patients who did not discontinue.	Missing data handled by model.	Assumes missing at random. Discontinued patients would have behaved similarly to patients who did not discontinue.
Sensitivity analysis 1	Based on the slope estimates for drug and placebo in patient subset 2.	Patients without a result would have behaved similarly to discontinued patients with a result who are in the same treatment group.	Based on the slope estimates for placebo patients in patient subset 2, but	Patients who died before week 52 would have behaved in a similar or worse way to a placebo patient who prematurely discontinued.
Sensitivity analysis 2	Based on the slope estimates for placebo in patient subset 2.	Patients without a result would have behaved similarly to discontinued placebo patients with a result.	truncated so that those who died are more severe.	
Sensitivity analysis 3	Based on the slope estimates for placebo in patient subsets 1 and 2.	Patients without a result would have behaved similarly to placebo patients with a result regardless of whether they prematurely discontinued treatment or not.	Based on slope estimates for placebo patients in subsets 1 and 2, but truncated so those who died are more severe.	Patients who died before week 52 would have behaved in a similar or worse way to a placebo patient regardless of whether they prematurely discontinued treatment or not.

Proprietary confidential information © 2018 Boehringer Ingelheim International GmbH or one or more of its affiliated companies

Further sensitivity analyses will be described in detail in the TSAP. Similar sensitivity analyses will be performed for the key secondary endpoints. In the analysis of all other continuous secondary endpoints, missing data will not be imputed. The mixed effect model will handle missing data based on a likelihood method under the "missing at random assumption". Following the intention-to-treat (ITT) principle, every randomised patient with at least one data point (at baseline or after randomization) will be included in this analysis. In the analysis of time to all-cause mortality, missing or incomplete data will be handled using censoring as detailed in the TSAP.

7.5.2 Safety endpoints

Missing or incomplete AE dates will be imputed according to BI standards. Other missing safety data will not be imputed.

7.5.3 Plasma concentrations

Descriptive statistics of concentrations at specific time points will be calculated only when at least 2/3 of the individuals have concentrations within the validated concentration range. The overall sample size to decide whether the "2/3 rule" is fulfilled will be based on the total number of samples intended to be drawn for that time point (i.e. BLQ, NOR, NOS, NOA are included).

